8.0 INVESTIGATOR RESPONSIBILITIES

8.1 Investigator Performance

The Principal Investigator and each Investigator will ensure that each subject is consented.

The study will be performed in full accordance with this protocol, the principles of the Declaration of Helsinki, ICH E6 Good Clinical Practice (GCP); and applicable local regulatory requirement(s).

8.2 Ethical Considerations

8.2.1 Ethics Committee Review and Approval

It is the responsibility of the Investigator or designee to submit the protocol, ICF/IAF, and subject information sheet, to an IRB/IEC for their review according to local regulation. All the required study documents must be approved by the IRB/IEC prior to the consent of the first subject. A copy of the IRB/IEC written approvals must be submitted to Circassia Ltd before the study may start. Written approval must be obtained from the IRB/IEC for all major changes to the protocol, except when necessary to eliminate apparent immediate hazard to the subject. In this case, the IRB/IEC should be notified as soon as possible and written approval obtained.

The study protocol will also be reviewed by the appropriate regulatory authority/authorities. The study will not proceed until the appropriate regulatory authority/authorities has/have granted a clinical study authorisation.

8.2.2 Written Informed Consent

Prior to enrolment, the study procedures and any known or likely risks will be explained to the subjects in lay language by the Investigator or designee. Subjects will also waive their right to the unblinding of study medication from CP007, as was previously stipulated in CP007. Any questions will be answered and subjects willing to participate, or their legally authorised representative, will provide written informed consent by reading and signing the ICF. Adolescent subjects will sign an IAF. Any adolescent subjects who turn 18 years of age while in this study will be asked to sign a new informed consent form at their next on-site visit. All subjects will receive a copy of the signed ICF(s), and if appropriate IAF(s), as well as written information sheets about the study. The subjects will be assured that they can withdraw from the study at any time and for any reason. Each subject's ICF/IAF must be signed and dated by both the Investigator or designee and the subject. The original signed ICF(s) and IAF(s) will be kept in the patient's medical file and a copy of the signed ICF(s)/IAF(s) will be given to the subject.

8.2.3 Information for Subject's General Practitioner

If the subject consents, their general practitioner (and any specialist the subject might be treated by) will be notified of the subject's intended involvement in the study.

8.3 Confidentiality

8.3.1 Subject Confidentiality

The Investigator shall reassure subjects that their identity will be kept confidential by third parties that conduct audits and inspections of the study centre and its documentation. A unique study number assigned to each subject at the start of the study will be used to identify the subject in the EDC system, on all study correspondence and in the study database.

8.4 Study Documentation

8.4.1 Case Report Forms

Data will be provided from electronically uploaded subject reported diaries and Investigator completed CRFs. Data will be periodically uploaded from the digital pen via secure web access from the site's/subject's home computer and the internet or via a mobile 'phone supplied specifically and for the sole purpose of uploading study data. Data on CRFs must correspond to and be supported by source documentation maintained at the study centre. All CRFs and records transmitted to the Sponsor must carry only coded identifiers such that personally identifying information is not transmitted. Access to the EDC system is available to authorised users via the study's Internet web site, where an assigned username and password are required for access.

Any changes made to data after collection will be made through the use of Data Clarification Forms. Data reported on the CRFs, which are derived from source documents, should be consistent with the source documents or the discrepancies should be explained. CRFs will be considered complete when all missing and/or incorrect data have been resolved.

An audit trail of all changes that are made to the database, including the reason for the data change, will be created and maintained.

The database is fully 21CFRpart11 compliant and provides a secure environment for subject data.

The Investigator will keep a copy of the CRFs, the Investigator's Site File and source documents until notified otherwise by Circassia.

8.5 Publication

Circassia intends to publish the results of this study, whether positive or negative, in line with the guidance in the Declaration of Helsinki. The Investigators and Circassia will normally prepare a manuscript together. To avoid disclosures that may affect the proprietary rights of the Sponsor, the Investigator agrees to allow Circassia the opportunity to review all manuscripts and abstracts 60 days prior to submission for publication. Circassia reserves the right to include the report of this study in any regulatory documentation or submission or in any informational materials.

8.6 Non-Protocol Research

No investigational research procedures pertaining to this study other than those outlined in this protocol may be undertaken on the subjects without the prior written permission of the subject, the Sponsor, the IRB/IEC and, when necessary, the appropriate regulatory authority.

9.0 SPONSOR RESPONSIBILITIES

9.1 General

Circassia agrees to adhere to the most current version of ICH E6 Guidelines on GCP. Circassia has a legal responsibility to report fully to regulatory authorities the results of this study.

9.2 No Fault Compensation and Indemnity

Circassia will provide “no-fault” compensation insurance against any injury incurred by a subject as a result of participation in the study. Circassia adheres to the ABPI “Clinical Trial Compensation Guidelines” (1991). The Investigators in this study will be indemnified as detailed in a separate document.

9.3 Monitoring

The study staff may not enter any subjects into the study prior to completion of an initiation meeting conducted by a representative of Circassia or designee.

Monitoring during the study will be undertaken at regular intervals by suitably qualified and appropriately trained personnel under contract to Circassia according to standard operating procedures. The monitoring will be conducted via on-site visits or remote monitoring. The purpose of the monitoring is to ensure:

- Compliance with the protocol;
- Adherence to regulatory and GCP obligations;
- Ensure filing of all study documents;
- The completeness of the data entered by sites and subjects;
- Accurate and timely reporting of AE(s) and SAEs
- Liaison with the Investigator and study staff to clarify any problems that may arise during the study.

9.4 Confidentiality

Neither Circassia nor its designee(s) will have access to any material on file referring to the study subject by their full name. The identity of the subject will be respected and maintained as confidential at all times.

The ePRO provider may hold personal information in a separate database, including name, address, email and mobile phone contact details. Only the ePRO provider will have access to this database. This information is required for:

- The potential dispatch of mobile ‘phones for those subjects without internet access
- The release of email and/or mobile ‘phone reminders and alerts.

Any collection or use of subject data will be in compliance with Data Protection requirements. Note, in Czech Republic, this personal information is not collected by the ePRO provider and only the site will hold this information.

The ePRO provider will ensure the databases are compliant with the clinical industry regulations and as such the confidentiality, integrity and accessibility of these systems are fully managed and controlled. Access to the data is provided only to specifically approved and authorised individuals for the duration of the study.

9.5 Finance

Financial agreements between Circassia, the Contract Research Organisation and the Investigator will be the subject of separate agreements.

9.6 Audit

Circassia may audit or appoint an independent auditor to conduct an audit of this study while it is running or after it has been completed. The study may also be inspected by a regulatory authority either while it is running or up to several years later.

11.0 APPENDICES

APPENDIX 1 Allergy Medication Plan

The “Allergy Medication Kit” is a package of medications that you may use during the period you are scoring your symptoms on the diary to relieve any troublesome allergy symptoms that you may experience. The kit will include the following allergy medications:

Allergy Medications for Allergy Symptoms (Rhinoconjunctivitis)		
Step	Allergy Medication	Dosing Instruction
1	Anti-Histamine Eye Drops (Ketotifen)	1 drop in each affected eye a maximum of twice a day
2	Anti-Histamine Tablets (Loratadine)	Maximum of 1 tablet a day
3	Steroid Nasal Spray (Fluticasone Propionate)	Maximum of 2 sprays (usually just one) in each nostril a day
4	Steroid Tablets (Methylprednisolone)	Not included in the Allergy Medication Kit but to be used as prescribed by the study doctor

Allergy Medication Plan

The Allergy Medication Kit contains three medicines that are commonly used by doctors to treat allergy symptoms (rhinoconjunctivitis). You should wait until your allergy symptoms become troublesome **before** using any of the provided medication. The Allergy Medication Kit medicines should be used as follows:

When your allergy symptoms are mainly ocular, such as itchy, watery, red or sore eyes.

If you mainly have ocular symptoms, wait until these become troublesome and then use the eye drops provided in the Allergy Medication Kit. If you find your ocular symptoms do not improve or they are still troublesome half an hour **after** using an eye drop take one of the anti-histamine tablets from the Allergy Medication Kit.

When you have nasal symptoms, such as runny nose, sneezing, blocked or itchy nose or when you have both nasal and ocular (eye) symptoms.

If you mainly have nasal symptoms, or nasal and ocular symptoms, treat them by taking one of the anti-histamine tablets from the Allergy Medication Kit. If you find your nasal symptoms do not improve or they are still troublesome two hours after taking the tablet use the steroid nasal spray included in the Allergy Medication Kit. If you find your ocular symptoms do not improve or they are still troublesome at two hours after using the tablet use your anti-histamine eye drops included in the Allergy Medication Kit.

## MODIFICATION HISTORY

Unique Identifier for this Version	Date of the Document Version	Author	Significant Changes from Previous Authorised Version
1.0	18OCT2016	[name]	Not Applicable – First Version
2.0	23FEB2017	[name]	
Added frequency and percentage of subjects included in each population to Section 9.
 
In Section 13.1.3 specified that all 21 days of symptom score recording is to be populated using each of the 3 methods of imputation
 
Clarified in Section 13.2.1.5 how subjects are defined as asthmatic or non-asthmatic
 
In Section 13.2.2.5 update the denominator used for percentage of subjects whose symptoms have been significantly worse in the past month
 
In Section 13.3.2.6 added the total number of doctor visits as well as the number and percentage of subjects with any visit to the doctor

Document: CP007A SAP.docx

Author: [name]

Version Number:

V 2.0

Version Date:

23 Feb 2017

Template No: CS\_TP\_BS016 – Revision 3

Reference: CS\_WI\_BS005

Effective Date: 01May2012

Copyright © 2012 Quintiles Transnational Corp. All rights reserved.

The contents of this document are confidential and proprietary to Quintiles Transnational Corp. Unauthorized use, disclosure or reproduction is strictly prohibited.

---

### LIST OF ABBREVIATIONS

ACQ	Asthma control questionnaire
AE	Adverse event
AIC	Akaike's information criterion
ANCOVA	Analysis of covariance
ASS	Mean Asthma Symptom Score
BOCF	Baseline Observation Carried Forward
CGM	Computer Graphics Metafile
CI	Confidence interval
CMH	Cochran-Mantel-Haenszel
CRF	Case Report Form
CS	Combined Score
ENR	Enrolled population
ePRO	Electronic Patient Reported Outcome
FAS	Full Analysis Set
GINA	Global Initiative for Asthma
LOCF	Last Observation Carried Forward
LS	Least squares
MAR	Missing at random
MedDRA	Medical Dictionary for Regulatory Activities
mITT	Modified Intent-to-Treat
MMRM	Mixed Model Repeated Measures
ODS	Output Delivery System
PAC3	Post Administration Collection Period 3
PSQI	Pittsburg Sleep Quality Index
PT	Preferred Term
RMS	Rescue Medication Score
RQLQ	Rhinoconjunctivitis Quality of Life Questionnaire
SAE	Serious adverse event
SAF	Safety
SAP	Statistical analysis plan
SOC	System Organ Class
TLF	Table, Listing, Figure
TNSS	Total Nasal Symptom Score
TOSS	Total Ocular Symptom Score
TRSS	Total Rhinoconjunctivitis Symptom Score
WHO-DD	World Health Organization-Drug Dictionary

Document: CP007A SAP.docx

Author: [name]

Version Number:

V 2.0

Version Date:

23 Feb 2017

Template No: CS\_TP\_BS016 – Revision 3

Reference: CS\_WI\_BS005

Effective Date: 01May2012

Copyright © 2012 Quintiles Transnational Corp. All rights reserved.

The contents of this document are confidential and proprietary to Quintiles Transnational Corp. Unauthorized use, disclosure or reproduction is strictly prohibited.

WOCF	Worst Observation Carried Forward
WPAI:CIQ-AS	Work Productivity and Activity Impairment Questionnaire plus Classroom Impairment Questions: Allergy Specific

Document: CP007A SAP.docx  
Author: [name]

Version Number: V 2.0  
Version Date: 23 Feb 2017

Template No: CS\_TP\_BS016 – Revision 3  
Effective Date: 01May2012

Reference: CS\_WI\_BS005

Copyright © 2012 Quintiles Transnational Corp. All rights reserved.

The contents of this document are confidential and proprietary to Quintiles Transnational Corp. Unauthorized use, disclosure or reproduction is strictly prohibited.

## 1. INTRODUCTION

This document describes the rules and conventions to be used in the presentation and analysis of efficacy and safety data for Protocol CP007A as set out in the latest version of the output shells. It describes the data to be summarised and analysed, including specifics of the statistical analyses to be performed.

This statistical analysis plan (SAP) is based on Protocol version 5 dated 08 December 2014.

## 2. STUDY OBJECTIVES

### 2.1. PRIMARY OBJECTIVE

The primary objective is to evaluate the continued efficacy of Cat-PAD, the first in a new class of Synthetic Peptide Immuno-Regulatory Epitopes, for a total of up to 5 years after the initial administration of treatment in Protocol CP007, based on the reduction of symptoms and the use of allergy medication in subjects previously participating in Protocol CP007.

### 2.2. SECONDARY OBJECTIVES

The secondary objectives are:

- To evaluate the continued safety and tolerability of Cat-PAD for up to 5 years after the administration of treatment.
- To evaluate the effect of Cat-PAD on the Rhinoconjunctivitis Quality of Life Questionnaire (RQLQ) for up to 5 years after the administration of treatment.
- To evaluate the effect of Cat-PAD on the onset of asthma for up to 5 years after the administration of treatment.
- To evaluate the effect of Cat-PAD on asthma progression in subjects previously enrolled in CP007 with Global Initiative for Asthma (GINA) 1 asthma for up to 5 years after the administration of treatment.

---

Document: CP007A SAP.docx

Author: [name]

Version Number:

V 2.0

Version Date:

23 Feb 2017

Template No: CS\_TP\_BS016 – Revision 3

Reference: CS\_WI\_BS005

Effective Date: 01May2012

Copyright © 2012 Quintiles Transnational Corp. All rights reserved.

The contents of this document are confidential and proprietary to Quintiles Transnational Corp. Unauthorized use, disclosure or reproduction is strictly prohibited.

### 2.3. EXPLORATORY OBJECTIVES

The exploratory objectives are:

- To evaluate the effect of Cat-PAD on changes in asthma control in asthmatic subjects for up to 5 years after the administration of treatment.
- To evaluate the effect of Cat-PAD on changes in sleep quality in adults using the Pittsburg Sleep Quality Index (PSQI) for up to 5 years after the administration of treatment.
- To evaluate the effect of Cat-PAD on changes in productivity using the Work Productivity and Activity Impairment Questionnaire plus Classroom Impairment Questions: Allergy Specific (WPAI:CIQ-AS) for up to 5 years after the administration of treatment.
- To evaluate the effect of Cat-PAD on symptomatology on unplanned exposure to a cat in normal daily life in subjects who no longer keep a cat for up to 5 years after the administration of treatment.
- To evaluate the effect of Cat-PAD on health economic outcomes for up to 5 years after the administration of treatment.

### 2.4. SAFETY OBJECTIVES

The safety and tolerability of Cat-PAD is to be assessed by measurement/recording of adverse events (AEs) and serious AEs (SAEs).

---

Document: CP007A SAP.docx

Author: [name]

Version Number:

V 2.0

Version Date:

23 Feb 2017

Template No: CS\_TP\_BS016 – Revision 3

Reference: CS\_WI\_BS005

Effective Date: 01May2012

Copyright © 2012 Quintiles Transnational Corp. All rights reserved.

The contents of this document are confidential and proprietary to Quintiles Transnational Corp. Unauthorized use, disclosure or reproduction is strictly prohibited.

### 3. STUDY DESIGN

#### 3.1. GENERAL DESCRIPTION

This is an optional, prospective, follow-on study to a randomised, double-blind, superiority, multiple dose, placebo-controlled, parallel group, multi-centre, field study (CP007). Subjects from participating sites who complete the final Post Administration Collection Period (PAC3) in CP007 are to be invited to participate in CP007A.

The population is to be limited to those subjects in the CP007 study and hence the maximum number to be enrolled in this study is the number of subjects randomised in CP007 which was 1408 subjects.

No additional investigational product is to be administered. Subjects will have received one of the following three study drug regimens in study CP007:

- Single course of Cat-PAD [4 doses of Cat-PAD 6 nmol (one dose administered every 4 weeks), followed by 4 doses of Placebo (one dose administered every 4 weeks), 4 x 6 nmol]
- Two courses of Cat-PAD [8 doses of Cat-PAD 6 nmol (one dose administered every 4 weeks), 8 x 6 nmol]
- Placebo [8 doses of Placebo (one dose administered every 4 weeks)]

In CP007, Cat-PAD and/or Placebo doses were administered every 4 weeks ( $\pm 2$  days) for 28 weeks (2 x 4 doses per subject).

Where possible, enrolment for CP007A is to occur at the same time as the final Follow-Up Visit as scheduled in CP007. Subjects who consent to take part in this study and who meet all inclusion/exclusion criteria are to be issued with paper diary binders and a digital pen (ePRO) or mobile phone to record the required subject reported outcomes data.

Subject reported outcomes are to comprise of monthly and annual evaluations.

On a monthly basis, subjects are to record information regarding:

- Hospital/doctor visits
- Lost work/school days
- Changes in home environment
- Exposure to cat

---

Document: CP007A SAP.docx  
Author: [name]

Version Number: V 2.0  
Version Date: 23 Feb 2017

Template No: CS\_TP\_BS016 – Revision 3  
Effective Date: 01May2012

Reference: CS\_WI\_BS005

Copyright © 2012 Quintiles Transnational Corp. All rights reserved.

The contents of this document are confidential and proprietary to Quintiles Transnational Corp. Unauthorized use, disclosure or reproduction is strictly prohibited.

- Global assessment of symptoms to cat exposure (only for subject no longer living with an indoor cat)
- Asthma progression
- Concomitant medication

The annual Allergy Evaluation Period for CO007A is defined as a 3-week (21 day) period, taking place at the same time of year as the 3-week Baseline Allergy Evaluation visit in CP007 (Visits 2A and 2B) and is to include:

- At the start of the 3-week Allergy Evaluation Period
  - o Diagnosis of asthma
- Daily recording for 3 weeks
  - o Rhinoconjunctivitis symptoms
  - o Asthma symptoms
  - o Allergy medication use
  - o Exposure to indoor cat
- At the end of the 3-week Allergy Evaluation Period
  - o Change in geographic location
  - o 6-Question asthma control questionnaire (ACQ) excluding lung function (for asthmatics only)
  - o RQLQ
  - o PSQI (if at least 18 years old at the time of assessment)
  - o WPAI:CIQ-AS

Subjects are to have up to four study visits each year, two of which may be conducted by telephone. At each visit, site staff will record any AEs and SAEs, and at the on-site visits subjects are to be provided with their next diary binder.

Subjects will have a final End of Study Visit, which will coincide with the end of the final annual Allergy Evaluation Period assessment.

The duration of this follow-up study is to be up to 4 years for each subject.

---

Document: CP007A SAP.docx  
Author: [name]

Version Number: V 2.0  
Version Date: 23 Feb 2017

Template No: CS\_TP\_BS016 – Revision 3  
Effective Date: 01May2012

Reference: CS\_WI\_BS005

### 3.2. SCHEDULE OF EVENTS

The schedule of events can be found in Section 6.1 of the Protocol.

## 4. PLANNED ANALYSES

There are four planned unblinded interim analyses.

The first analysis of the data is to be performed on the first year's data after all subjects have either

- Completed their year 1 annual assessment in CP007A
- Discontinued prior to their year 1 annual assessment
- Progressed beyond their year 1 annual assessment regardless of the completion of the assessment

Additional analyses of the second, third and fourth year in the study are to be performed for each relevant year based on the same criteria as above. Analysis of the later years will only be performed if there was a positive outcome in the previous years.

The Quintiles study team, including those responsible for creating the programs to produce the outputs for each analysis, will remain blinded. Once the programs have been produced by the blinded Quintiles study team, these programs are to be sent to an independent statistician at a different geographical location than the blinded team, who will apply the randomisation schedule and provide Circassia with a set of unblinded outputs each year.

Details on independent unblinded team members within Quintiles to perform the analysis and members within Circassia authorised to receive unblinded outputs are specified in a separate Unblinding Plan document.

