7.4 Statistical Analysis

Further detail of the statistical analyses and data presentations to be used in reporting the study, including dictionaries used for coding and software used, will be provided in the Statistical Analysis Plan (SAP), which will be approved by Circassia prior to performing any analysis of the data.

The nature of the formal statistical testing will be described and justified in the SAP, discussing any potential biases and challenges caused by the data collected and circumstances of the study. It is anticipated that the analyses will be similar to those performed for the CP007 study. For the primary hypothesis testing versus placebo a Bonferroni-Holm procedure will be used to adjust alpha in order to compensate for multiplicity when comparing the two Cat-PAD treatment arms versus placebo, thereby keeping the overall type I error rate at 0.05. The Bonferroni-Holm procedure will assess each of the two treatment comparisons (two courses of Cat-PAD versus placebo and one course of Cat-PAD versus placebo), whereby the smallest p-value (of the two treatment comparisons) will be tested at the 0.05/2 (i.e. $p < 0.025$) alpha level. If this first comparison is statistically significant then the remaining treatment comparison p-value will be tested at the 0.05 alpha level. The tests will be two sided.

If any parametric analyses are found to be inappropriate and/or fail their assumptions then supportive analysis will include non-parametric methods, as appropriate.

All data will be summarised to include the mean, N, SD, median, minimum and maximum values for continuous variables and frequencies and percentages for categorical variables.

The first analysis of the data will be performed on the first year's data after all subjects have completed one year in this study. Additional analyses of the second, third and fourth year in the study will be performed after all subjects have completed each additional year in the study. At each of the statistical analyses performed after one, two, three and four years, there will be no adjustment to the significance level, apart from the Bonferroni-Holm correction (due to multiple treatment comparisons) stated above, because analysis of the later years will only be performed if there was a positive outcome in the previous years, and this is, therefore, a hierarchical analysis.

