### 4.1. FINAL ANALYSES

All final, planned analyses identified in this SAP are to be performed by Quintiles Biostatistics.

The following events are prerequisites for the production of any of the four interim analyses planned.

- Sponsor authorisation of the SAP and Table, Listing, Figure (TLF) shells
- Quintiles authorisation of final locked database snapshot

---

Document: CP007A SAP.docx  
Author: [name]

Version Number: V 2.0  
Version Date: 23 Feb 2017

Template No: CS\_TP\_BS016 – Revision 3  
Effective Date: 01May2012

Reference: CS\_WI\_BS005

For each interim analysis Quintiles Biostatistics will extract all data as entered in the relevant year's diary binder of each subject (there is a separate diary binder for each analysis year).

After cleaning (no outstanding data queries) of the relevant analysis year's data by DataMatica and authorisation by Quintiles Biostatistics as well as coding of all AEs and concomitant medications by Quintiles Coding, the final locked database snapshot for the relevant interim analysis (year 1, year 2, year 3 or year 4) is to be provided by DataMatica to Quintiles for the purpose of producing the interim analysis.

AEs entered in the Adverse Event Case Report Form (CRF) are to be cumulative and will not be assigned to a specific year for analysis.

- Sponsor authorisation of analysis sets

Prior to each interim analysis Quintiles Biostatistics will programmatically prepare listings of all subjects and their status with regards to inclusion or exclusion from each analysis population based on the definitions of each analysis population as described in [Section 5: Analysis Sets](#).

The listings are to be provided to Circassia for authorisation prior to each interim analysis.

---

Document: CP007A SAP.docx

Author: [name]

Version Number:

V 2.0

Version Date:

23 Feb 2017

Template No: CS\_TP\_BS016 – Revision 3

Reference: CS\_WI\_BS005

Effective Date: 01May2012

Copyright © 2012 Quintiles Transnational Corp. All rights reserved.

The contents of this document are confidential and proprietary to Quintiles Transnational Corp. Unauthorized use, disclosure or reproduction is strictly prohibited.

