## 7.4. MULTIPLE COMPARISONS/MULTIPLICITY

For the primary hypothesis testing vs. Placebo a Bonferroni-Holm procedure is to be used to adjust alpha in order to compensate for multiplicity when comparing the two Cat-PAD treatment arms vs. Placebo, thereby keeping the overall type I error rate at 0.05. More detail on the procedure is described in [Section 13.1.2: Primary Analysis of Primary Efficacy Variable](#).

Multiple analyses are to be performed as specified in [Section 4: Planned Analyses](#). At each of the statistical analyses performed after one, two, three and four years, there is no adjustment to the significance level, apart from the Bonferroni-Holm correction (due to multiple treatment comparisons) stated above, because analysis of the later years will only be performed if there is a positive outcome in the previous years, and this is, therefore, a hierarchical analysis.

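### The efficacy gate on Years 2 to 4 is worded to stop all analysis, so after a non-positive year no lock or output is scheduled for later RQLQ, asthma or adverse event data

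*SAP*

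**What the plan says.** SAP section 4 lists the analyses: "There are four planned unblinded interim analyses", one per year. It then adds: "Analysis of the later years will only be performed if there was a positive outcome in the previous years".

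Protocol 7.4 and SAP 7.4 give the same condition as the reason for making no alpha adjustment between years: "because analysis of the later years will only be performed if there was a positive outcome in the previous years" (protocol) and "because analysis of the later years will only be performed if there is a positive outcome in the previous years" (SAP). Both conclude that the approach is hierarchical. The protocol synopsis lists the later-year analyses with no such condition.

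SAP 4.1 is headed as covering final analyses, but it introduces its requirements with "The following events are prerequisites for the production of any of the four interim analyses planned". The diary extraction, cleaning, coding and locked snapshot it describes all belong to those four interims. Adverse events "are to be cumulative and will not be assigned to a specific year for analysis".

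None of the three places says what counts as a positive outcome. The nearest rule is in SAP 13.1.2: the study succeeds if at least one active arm differs significantly from placebo under Bonferroni-Holm.

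**The concern.** A hierarchical argument justifies withholding a confirmatory test when an earlier one has failed. It does not justify withholding RQLQ estimates, asthma summaries or adverse event tables. The gate is nevertheless placed on analysis as such, and no other time point for producing outputs is given.

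Follow-up does not stop because the gate closes. Protocol 4.7 ends the study after the four-year assessment, and protocol 4.6 allows earlier termination for safety or administrative reasons. Adverse events are collected until completion or withdrawal. The objectives on safety, RQLQ, asthma onset and asthma progression (protocol 2.2, SAP 2.2) carry no efficacy condition.

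The gap is most likely to appear when the treatment does not work, and complete long-term safety and asthma reporting is still owed in that case. The decision to report would then fall after unblinded results had reached the sponsor's authorised recipients.

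**Working it through.** **1. The passages side by side**

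| Topic | Conditional on efficacy? | Where |
|---|---|---|
| Analysis of Years 2 to 4 | Yes | SAP 4, SAP 7.4, protocol 7.4 |
| Analysis of Years 2 to 4 | No condition stated | Protocol synopsis |
| Locks and outputs | Only for the four interims | SAP 4, 4.1 |
| Five-year safety, RQLQ and asthma objectives | No | Protocol 2.2, SAP 2.2 |
| Safety summaries | No, but no time point given | Protocol 7.4.3, SAP 14 |
| RQLQ and asthma methods | No, but no time point given | SAP 13.2.2.4, 13.2.2.5 |

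The methods exist. What is missing is an occasion to run them once the gate has closed. Adverse events up to the last snapshot are covered because they are cumulative; later ones are not.

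**2. Later data may already be held at the Year 1 analysis.** The Year 1 trigger allows for subjects who have "Progressed beyond their year 1 annual assessment regardless of the completion of the assessment". One prerequisite for any interim is "Sponsor authorisation of the SAP and Table, Listing, Figure (TLF) shells". The first SAP version is dated 18 October 2016 and the planned start was December 2013: (2016 − 2013) × 12 + (10 − 12) = 34 months. A subject enrolled at the planned start would by then be past Year 2. Actual enrolment dates are not given.

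**3. Reproducing the protocol's power.** Inputs from protocol 7.2: difference 0.525 (25% of 2.10), SD 1.29, two-sided alpha 0.025 (critical value 2.241). SE = 1.29 × √(2/n).
- n = 266: SE = 0.1119; 0.525/0.1119 = 4.693; Φ(4.693 − 2.241) = 0.993. Stated: at least 99%.
- n = 130: SE = 0.1600; 0.525/0.1600 = 3.281; Φ(3.281 − 2.241) = 0.851. Stated: at least 80%.

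Both figures are confirmed.

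**4. Probability that the gate closes at Year 1.** Assume that positive means the SAP 13.1.2 rule. The gate closes when both |Z| values are below 2.241. (Z1, Z2) is bivariate normal with means effect/SE and correlation 0.5 from the shared placebo arm.

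| Effect in both arms | 266 per arm | 130 per arm |
|---|---|---|
| 0 | 95% | 95% |
| 0.20 | 53% | 74% |
| 0.30 | 18% | 49% |
| 0.42 (20% of 2.10) | 2% | 20% |
| 0.525 | 0.1% | 6% |

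With only one arm effective at 0.525, closure is 0.6% at 266 per arm and 14% at 130.

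**5. Probability that Year 4 is never analysed.** Simulation, constant effect in both arms, assumed between-year correlation 0.3 to 0.7.
- Effect 0.525: 0.2% with 266 per arm every year; 1.8% to 1.9% if n falls linearly from 266 to 130 by Year 4; 12% to 15% with 130 every year.
- Effect 0.30: 32% to 40%, 46% to 55% and 69% to 80% respectively.

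**6. The gate is not stated per arm.** Simulation: one arm effective at 0.525 in every year, the other null, 266 per arm, Holm within each year, same correlations. The table gives the chance of at least one false rejection for the null arm over four years.

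| Gate | Two-sided | Favouring Cat-PAD |
|---|---|---|
| Opens if either arm was significant | 13% to 17% | about 6.5% to 8.6% |
| Applied to each arm separately | about 5% | about 2.5% |

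**The case against.** The strongest reply is that the gate concerns testing only. In both 7.4 sections it explains why alpha is not adjusted, and SAP 4 repeats the sentence without the reason. Other text is unconditional: protocol 7.4.3 and SAP 14 call for safety summaries, SAP 14.1 for listings of all adverse events, SAP 13.2.2.5 for asthma counts at each annual assessment, and SAP Appendix 1 for display labels for Years 01 to 04. SAP 4 also speaks of unblinded outputs each year. This may well be the intent, but none of it creates a lock or output outside the four gated interims. The documents still conflict, and the operative word in three places is analysis.

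A reader might infer that later safety data would go unreported, or that the sponsor is free to suppress them. The documents do not support that. Expedited reporting of serious events continues (protocol 6.4.2.4), the sponsor acknowledges a duty to report fully to regulators (9.1), and it intends to publish whatever the result (8.5). These provisions limit discretion, although they schedule nothing.

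A reader might also infer that a result favouring placebo would open the gate, because SAP 13.1.2 states no direction. That is thin: 13.1.2 is not linked to the gate, the gate's own word is positive, and the primary objective concerns a reduction in symptoms and medication use.

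It is fair to say that closure is rare under the planned effect, and that a gate on testing ought to close when there is no effect. The synopsis omission is minor on its own.

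**Conclusion.** The point stands as one of scope and scheduling. Followed as written, the plan provides no lock or output for later-year RQLQ and asthma data, or for adverse events after the last snapshot, once a year is not positive. If follow-up stops when the gate closes, the gap shrinks to later data already collected.

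The closure figures (95% with no effect; 18% to 49% at 0.30; 0.1% to 6% at 0.525) assume the SAP 13.1.2 rule, SD 1.29, equal effects in both arms and no gain from covariate adjustment. They are probabilities that the gate closes and should not be read as probabilities that data are lost.

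The per-arm issue is secondary and depends on an any-arm reading, which the documents neither state nor exclude. The 13% to 17% should not be read as the rate of false efficacy claims; only about half favours Cat-PAD. The Year 1 primary test is unaffected.

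**What to change.** In SAP 4, SAP 7.4 and protocol 7.4, replace the gate sentence with text to this effect:

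- The gate applies only to confirmatory testing of the primary endpoint.
- A comparison is positive in a year if it is significant under SAP 13.1.2, in favour of Cat-PAD, in the FAS.
- An arm is tested confirmatorily in a later year only if that same arm was positive in all previous years. An arm no longer tested counts as not significant in the Holm procedure.
- Whatever the primary result, all data collected are locked at study end at the latest. Cumulative AE and SAE summaries, RQLQ, asthma, other secondary and exploratory outputs, and primary estimates with 95% CIs, are produced for every year with data.
- After a closed gate these outputs are descriptive, and any p-values are labelled non-confirmatory. The label is needed because SAP 13.2.2.1 to 13.2.2.4 test each secondary comparison at 0.05 without Holm.

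Bring the synopsis into line.

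If the remaining error is stated, give both figures. With one arm effective at 0.525 in Year 1 only and everything else null, the two-sided error over both arms and all years is about 7%, of which about 3.6% is false claims in favour of Cat-PAD. Testing each arm's sequence at 0.025 throughout is therefore not needed in that scenario to hold false efficacy claims below 5%.

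The cost is a SAP revision, a protocol wording change, at least one further cleaning, coding and lock cycle after a closed gate, and re-runs of existing programs. The confirmatory claim becomes slightly stricter: an arm that misses one year cannot be claimed in later years, even if the other arm was positive.
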